
65 **Aim 1:** To examine the safety, feasibility, and PTSD symptom reductions associated with CBD (n=12) vs. placebo (n=12)
66 in 24 individuals receiving 10 daily sessions of mPE as a standard of care for PTSD.

67 Hypothesis 1: Combining CBD with mPE will be safe based on minimal (< 5%) adverse events and no serious adverse
68 events related to treatment in the study.

69 Hypothesis 2: A CBD vs. placebo trial design will be feasible defined as 75% or more of assessed individuals meeting
70 all eligibility criteria and 80% or more of CBD participants completing all 10 mPE sessions.

71 Hypothesis 3: Participants in the CBD condition will have greater treatment-related PTSD reductions than placebo as
72 measured by the Clinician Administered PTSD Scale (CAPS-5)³ and PTSD Checklist (PCL-5).⁴

73 **Aim 2:** To evaluate biochemical and physiological levels associated with the eCB system and stress response in CBD vs.
74 placebo.

75 Hypothesis 4: Participants in the CBD condition will have higher levels of AEA and 2-AG, and lower levels of cortisol
76 than placebo following treatment.

77 Hypothesis 5: Participants in the CBD condition will have lower average heart rate during exposure therapy sessions
78 than placebo.

79 **Aim 3:** To determine the association between changes in biomarker levels (cortisol, AEA, 2-AG), physiology (heart rate),
80 and PTSD symptom reduction following treatment.

81 Hypothesis 6: Reductions in cortisol and increases in AEA and 2-AG will be associated with PTSD symptom reductions
82 following treatment.

83 Hypothesis 7: Lower average heart rate observed during exposure therapy sessions will be associated with PTSD
84 symptom reductions following treatment.

85 **4. MILITARY RELEVANCE**

86 As compared to civilians, the rate of PTSD is particularly elevated among military populations, with approximately 23% of
87 military vs. 6-8% of civilians meeting criteria for PTSD.⁵ PTSD has been identified as the signature deployment-related
88 psychiatric condition among service members. The functional impact of PTSD can cost service members their military
89 careers and veterans with PTSD are at increased risk of unemployment and homelessness following military separation.⁶
90 Notwithstanding evidence that PE is an effective treatment for PTSD, there remains room for improvement in outcomes
91 given that a large proportion of patients (~50%) fail to significantly benefit from treatment.⁷ This issue is especially

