178 system since research has shown that CBD may have low affinity for CB receptors, but nonetheless is able to bind to
179 CB1.³⁹ CBD may also act as an antagonist to other agonists due to effects at different prejunctional sites and indirect
180 interactions with non-cannabinoid receptors.⁴⁰ In turn, this may explain possible effects on eCB metabolism including
181 inhibition of the uptake and degradation of critical eCBs associated with stress response including AEA and 2-AG.

[figure not shown]
182 **Innovation.** Additional research is warranted to fully understand the benefits of CBD for PTSD. Currently, there are no
183 published clinical trials investigating the efficacy of CBD in reducing PTSD and existing PTSD literature in humans only
184 includes healthy individuals or case study data. Research on cannabinoids and PTSD remains in the early stages of
185 development and more research is needed to understand how CBD modulates the eCB system. Based on existing
186 research, the next logical step is to investigate CBD as an augmentation treatment for an established psychotherapy that
187 targets extinction learning mechanisms for PTSD symptom reduction. This proposal will examine CBD as an adjunct for
188 mPE and explore potential biological mechanisms for its effect, making it the first study of its kind. Findings from this study
189 have the potential to improve outcomes among military and civilians with PTSD and mitigate the personal, social, and
190 economic costs of this debilitating, chronic condition. This study will also expand understanding of the relationship
191 between PTSD, CBD, and the eCB system.

192 6. RESEARCH DESIGN

193 This study is an early Phase II double-blind, pilot randomized controlled clinical trial. We will use a permuted block
194 randomization design stratified by PTSD severity median score of 51 on the PCL-5 and population type (military or
195 civilian). The median score stratification was derived from a recently completed STRONG STAR randomized clinical trial
196 of military veterans seeking treatment for PTSD (manuscript in press). The decision to stratify by population was based on
197 existing literature that has found differences in treatment response between military and civilian samples (e.g., Steenkamp
198 et al., 2015; [name] et al., 2019). Participants will be 24 individuals with PTSD to investigate the safety, feasibility, and

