7. RESEARCH PLAN

7.1 Selection of Subjects

Number of subjects to be screened for eligibility: 40

Target number randomized: 28

Target enrollment number for completers: 24

7.1.1. Subject Population.

Individuals between 18-65 years old recruited from the San Antonio community will be invited to participate in this research.

Efforts will be tailored to equally recruit diverse individuals across sex, gender/sexual orientation, race, age, disability, socioeconomic status, national origin, and branch of military service.

7.1.2. Inclusion and Exclusion Criteria.

Inclusion Criteria

1. Individuals between the age of 18 to 65 years old at time of screening.
2. Able to write, read, and speak English
3. PTSD diagnosis as assessed by Clinician-Administered Posttraumatic Stress Scale (CAPS-5)
4. Stable medication regimen for at least four weeks prior to the onset of study participation.

Exclusion Criteria

1. History of opiate, cocaine, methamphetamine, benzodiazepine, or cannabis abuse as determined by the National Institute of Drug Abuse Quick Screen (NIDA-Q).
2. Currently using opiates, cocaine, methamphetamines, benzodiazepines, or cannabis as evidenced by a positive urine drug screen prior to enrollment.
3. Currently pregnant as determined by a positive urine pregnancy test prior to enrollment.
4. Current clinically significant alcohol abuse in the past two weeks on the Quick Drinking Screen (QDS).
5. Currently breastfeeding.

238 6. Ongoing illness or physical health problem(s) that may be exacerbated by CBD (e.g., history of liver problems)
239 7. History of significant allergic condition, significant drug-related hypersensitivity, or allergic reaction to
240 cannabinoids.
241 8. Regular use of the following concomitant medications because of the possible interaction with CBD
242 • The anti-convulsant/anti-epileptics Carbamazepine and Phenytoin
243 • The atypical antipsychotics Olanzapine, Quetiapine, and Risperidone
244 • The entire class of barbiturates (Sedative-Hypnotics)
245 • Chronic, daily use of any class of benzodiazepines. Intermittent or as needed dose of a benzodiazepine will
246 be allowed.
247 • The miscellaneous hypnotics Zaleplon, Zolpidem, Eszopiclone, Ramelteon, and Suvorexant
248 • The herbal supplement St. John's Wort.
249 • The entire class of glucocorticoids
250 • Use of platelet inhibitors Clopidogrel and Warfarin unless the participant is on a stable dose.
251 • The antiretrovirals Ritonavir and Indinavir

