 483 monitoring. Secondary endpoints are listed in the table in Section 7.3 and include associated psychopathology, such as
 484 severity scores on measures of depression, general anxiety, disability, and PTSD-related cognitions.

485 **Biospecimens & Heart Rate Monitoring Measures:** We will also assess possible biochemical and physiological
 486 outcomes associated with treatment (Aim 2) and evaluate the relationship between changes in biochemical/physiological
 487 measures with PTSD symptom reductions (Aim 3). To address these aims we will collect blood and saliva samples and
 488 heart monitoring data via a wearable device as described in 7.3.1

489 7.4.3. Data analysis.

490 This pilot study was not powered for formal efficacy or mechanistic hypotheses testing.⁴² Our primary interests are to evaluate
 491 the safety and feasibility of the proposed recruitment, assessment, and treatment protocols; and to detect a signal of possible
 492 PTSD symptom reductions associated with CBD in preparation for a larger trial. To inform future studies, we will calculate
 493 conventional effect sizes with 95% confidence interval limits. Hedges' g will be used to calculate continuous outcome effect
 494 sizes (e.g., CAPS-5, PCL-5). Hedges' g has been recommended over Cohen's d for small samples based on sample size
 495 adjustments yet can be interpreted using the same conventional recommendations as Cohen's d.⁴³

496 Although the statistical power of this study is limited, we will perform statistical analyses appropriate for an adequately
 497 powered study to identify data analysis issues germane to future planning (e.g., data management and scoring, missing
 498 data, data distributions, outliers, trends over time, covariance structures). Statistical analyses will be intent to treat. We will
 499 complete descriptive statistics to describe the study sample and address the feasibility and safety hypotheses. Continuous
 500 outcome measures related to symptom changes and comparison of baseline and posttreatment means will be done with
 501 general or generalized linear mixed effects regression models with repeated measures, with fixed effects of time, group,
 502 and the group by time interaction. Measures with data collected during treatment will also be included in models. Little's⁴⁴
 503 missing completely at random analysis will be completed to confirm likelihood-based model assumptions. Pearson

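### Section 7.4.3 has no baseline covariate in the one-month symptom comparison; adding one costs almost nothing and may narrow the 95% confidence interval

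*Combined protocol and SAP*

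**What the plan says.** Under 7.4.3, analysis of continuous "outcome measures related to symptom changes and comparison of baseline and posttreatment means will be done with" "general or generalized linear mixed effects regression models with repeated measures, with fixed effects of time, group" and the interaction of the two. Scores taken during treatment join as further responses. The section lists no baseline covariate, no constraint that the arms share a baseline mean, and neither randomisation factor.

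The same section promises "conventional effect sizes with 95% confidence interval limits", using Hedges' g for CAPS-5 and PCL-5, and says "Statistical analyses will be intent to treat". It does not say which contrast g summarises, which SD standardises it, or whether time is categorical.

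Hypothesis 3 (Section 3) implies a comparison of change: "Participants in the CBD condition will have greater treatment-related PTSD reductions than placebo as" measured by CAPS-5 and PCL-5. Section 7.4.2 names both totals among the primary outcome variables. The Section 7.3 table and Section 14.0 place CAPS-5 at baseline and one month only; PCL-5 is also taken at three interim assessments. Section 6 describes a "randomization design stratified by PTSD severity median score of 51 on the PCL-5 and population type (military or" civilian), in blocks of four.

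**The concern.** With two time points and complete data, the saturated time-by-group model gives two possible arm contrasts: the raw one-month difference ΔY, and the interaction ΔY − ΔX, where ΔX is the chance baseline difference. The baseline-adjusted difference is ΔY − bΔX, with b the slope of follow-up on baseline. Hence

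change contrast = adjusted difference + (b − 1)ΔX.

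Baseline is therefore not ignored by the interaction, but it is subtracted with a fixed slope of 1. That is efficient only if the true slope is near 1. The raw one-month contrast fixes the slope at 0. The PCL-5 one-month contrast has the same form if time is categorical.

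After safety and feasibility, the effect sizes and their intervals are what the pilot hands to a larger trial. With 24 patients they are wide, so precision available from data already collected is worth having. The undefined g matters as well, because the candidate definitions give intervals of different width.

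**Working it through.** **Inputs from the plan.** 12 per arm (Section 2), 24 completers (7.1), 28 randomised with 4 lost (7.4.1), stratified blocks of four (Section 6), 95% intervals (7.4.3). The plan gives no interval width, SD or correlation to reproduce. Its recruitment figures do reproduce: 24 + 4 = 28 and 28/(1 − 0.30) = 40. The 17% dropout is 4/24; as a share of those randomised it is 4/28 = 14.3%.

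**Assumed.** Baseline-to-follow-up correlation ρ of 0.3, 0.5 or 0.7; ratio r of follow-up SD to baseline SD from 0.8 to 1.5; an even military/civilian split with no population effect. The slope is b = ρr.

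**Step 1: closed form, ignoring stratification.** In one-month SD units the 95% half-width is t√(2V/12), with
- raw one-month means: V = 1, t = 2.0739 (22 df)
- difference in change: V = 1 + 1/r² − 2ρ/r, t = 2.0739 (22 df)
- baseline-adjusted: V = (1 − ρ²)(1 + 1/20), t = 2.0796 (21 df)

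At r = 1 and ρ = 0.5 the first two both have V = 1 and half-width 0.847. The adjusted V is 0.75 × 1.05 = 0.7875, half-width 0.753, which is 11% narrower. At r = 1.25 the change half-widths are 0.912/0.776/0.611 for ρ = 0.3/0.5/0.7, against 0.830/0.753/0.621 adjusted: ratios 0.910/0.971/1.018.

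The most adjustment can cost here is √1.05 × 2.0796/2.0739 = 1.0275, or 2.8%. Against raw means it pays once |ρ| exceeds about 0.23. In large samples V(change) − V(adjusted) = (1/r − ρ)², so the gain over change vanishes when ρr = 1.

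**Step 2: simulation with the trial's stratified blocks** (n = 24, 6,000 runs per cell). Ratio of adjusted to comparator interval width. The first figure takes the outcome's own baseline as stratifier (PCL-5); the second has baseline correlated 0.7 (assumed) with the stratifier (nearer CAPS-5). The last row gives the range over all SD ratios.

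| Comparator | ρ = 0.3 | ρ = 0.5 | ρ = 0.7 |
|---|---|---|---|
| Change, r = 0.8 | 0.714, 0.722 | 0.759, 0.768 | 0.798, 0.806 |
| Change, r = 1.0 | 0.813, 0.820 | 0.872, 0.883 | 0.933, 0.939 |
| Change, r = 1.25 | 0.895, 0.904 | 0.955, 0.963 | 1.003, 1.010 |
| Change, r = 1.5 | 0.943, 0.950 | 0.995, 1.002 | 1.012, 1.019 |
| Raw one-month means, any r | 0.964–0.972 | 0.872–0.883 | 0.717–0.728 |

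Adding a non-prognostic population type gives back 0.4–0.7 points of width.

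**Step 3: true precision.** Stratification already balances part of baseline, but the unadjusted standard error takes no credit for it; unadjusted coverage runs from 94.7% to 98.1%. Part of the narrowing therefore corrects a conservative interval. True variance ratios (adjusted to change) at ρ = 0.5 give these equivalents:
- r = 1: 24/0.895 = 26.8 and 24/0.841 = 28.5 patients
- r = 1.25: 24/0.975 = 24.6 and 24/0.939 = 25.6
- r = 1.5: 24/1.009 = 23.8 and 24/1.012 = 23.7

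**Step 4: which SD ratio is plausible.** Entry requires a diagnosis ("PTSD diagnosis as assessed by Clinician-Administered Posttraumatic Stress Scale (CAPS-5"), and Section 4 motivates the trial "given that a large proportion of patients (~50%) fail to significantly benefit from treatment". If half the patients improve by d more baseline SDs than the rest, r = √(1 + d²/4): 1.12, 1.25 and 1.41 for d = 1, 1.5 and 2. Width ratios against change (4,000 runs) are then 0.902–0.954 at slope 0.5, 0.956–0.989 at slope 0.7 and 1.000–1.016 at slope 0.9.

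**Step 5: Hedges' g.** With the pooled one-month SD, equal SDs and true g of 0, mean interval widths at ρ = 0.3/0.5/0.7 are 2.00/1.69/1.30 (change), 1.66/1.66/1.65 (raw) and 1.60/1.47/1.20 (adjusted). Adjusted coverage is 95.4–96.7% (true g 0 and 0.5). Standardising by the residual SD instead would multiply g by 1/√(1 − ρ²) = 1.05/1.15/1.40.

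**Step 6: dropout.** With 28 randomised and 4 lost at random, the variance ratio against the planned likelihood contrast at equal SDs is 0.849/0.908/0.960 (first stratifier case) and 0.760/0.876/0.932 (second).

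**The case against.** The planned model is a valid, standard choice, and the plan says the pilot is not powered for efficacy. Nothing here is an error, and the size of the gain cannot be fixed from the documents. That is right, and it is why the point is optional.

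Equal SDs flatter the change comparison. At SD ratios above 1, which this population makes plausible, the gain at ρ = 0.5 falls to about 4% or nothing, and at ρ = 0.7 there is a loss of up to 2%. Interval width also overstates the information gained: at equal SDs and ρ = 0.5 the true standard error falls by 5–8% (√0.895 = 0.946, √0.841 = 0.917), not 12–13%. Both points stand.

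If g is meant to use one-month means, the gain at ρ = 0.3 is only 3–4%, and a low enough correlation removes it. That also stands, and it shows why the contrast must be named.

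The simulations use two time points, whereas PCL-5 has five. Under a random-intercept model pooling all five, without stratification, the gain is 14/9/3% at ρ = 0.3/0.5/0.7, against 17/11/5% with two. The PCL-5 figures are therefore approximate.

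Finally, keeping baseline-only participants adds no information on CAPS-5: with two time points the constrained-baseline estimate equals the completers' adjusted estimate. This removes one argument for that form of the fix and leaves the gain over the change contrast untouched.

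**Conclusion.** The point holds, as an optional improvement. The plan uses baseline with a slope fixed at 1 or not at all, depending on a contrast it does not name. Estimating the slope costs one degree of freedom. Over the assumed correlations and SD ratios, the adjusted interval runs from 29% narrower to about 2% wider than the interval for the difference in change (up to 3% wider with population type added). Against raw one-month means it is 3–28% narrower. At a correlation of 0.5, the 24 patients count as 27–29 with equal SDs, 25–26 at an SD ratio of 1.25, and 24 at 1.5.

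These sizes rest on correlations and SDs that the documents do not supply, so confidence in the amount is moderate. That the cost is small does not depend on them. No bias, invalid inference or sample-size error is implied. The missing definition of Hedges' g needs settling whichever contrast is chosen.

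**What to change.** In 7.4.3:

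- Define the CAPS-5 and PCL-5 effect as the one-month arm difference adjusted for the continuous baseline score, or from a model in which both arms share one baseline mean. The second form keeps participants with only baseline data in the intent-to-treat set.
- State that time is categorical and that small-sample degrees of freedom are used.
- Base Hedges' g on that adjusted difference, divided by a stated raw SD such as the pooled one-month SD, not the residual SD. With d the standardised difference before correction and J the small-sample factor, take the variance as J²[(SE/SD)² + d²/(2 × 22)]. Here 22 is 24 completers less 2 and should follow the number actually observed. State the critical value; the widths above are consistent with a t multiplier.
- Treat population type as an optional second covariate if both levels are adequately filled.

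The cost is two or three sentences and one degree of freedom (two with population type), with no new data. If the slope turns out near 1, the interval may be up to about 2% wider, or 3% with population type.

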** Daily Adverse Event monitoring to occur if participant taking one of the identified medications warranting additional monitoring. See Section

372

373

7.3.1 Collection and Storage of Human Biological Specimens.

374

Urine drug and pregnancy screen tests will be conducted at baseline for screening eligibility purposes.

375

376

Blood will be collected at four time points for a study total of about 28mLs. Approximately, 7mL of blood will be collected by venous puncture using a 7 mL EDTA blood collection tube immediately prior to the pretreatment medication review, and at interim assessments 1 (prior to PE session 1), 2 (prior to PE session 5), and 3 (prior to PE session 10). Blood will be immediately chilled in a cooler filled with ice.

377

378

379

380

Saliva will also be collected at four time points via passive drool. At the medication review appointment participants will be given a kit with salivette test tubes and instructions on how to collect early waking saliva samples (cortisol) upon waking. Saliva collections will be completed upon waking the day after the medication review appointment, and the day of sessions 1, 6, and 10. Participants will be instructed to immediately refrigerate the sample and bring it to the next scheduled appointment. Saliva samples will be collected from the participant by study staff when the participant arrives for their appointment and immediately chilled in a cooler filled with ice. Samples will be frozen at or below -20°C upon arrival at the Biological Psychiatry Analytic Laboratory (BPAL).

381

382

383

384

385

386

387

388

389

390

391

392

393

394

395

396

397

398

399

400

Biological specimens will be coded when collected from the participant by the study staff with a digital bar code that can be linked to the study and subject only by key-codes maintained by the STRONG STAR Data and Statistics Services.

Heart rate will be monitored using a wearable device placed on the right wrist, and elevations will be recorded continuously during sessions 3, 6, and 10 to obtain an objective measure of arousal to assess possible within- and between- session extinction learning in response to rehearsal of the individual's primary traumatic event. This data can be beneficial for individuals who report subjectively being more aroused during the exposure or behaviorally appear to be more activated.

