450 devices are monitored by state-of-the-art monitoring applications that include configuration audit, management, and
451 availability 24x7.

458 The UTHSA STRONG STAR data server is currently a VMware Instance running Windows Server 2016 Enterprise
 459 Standard with daily backup services and vSphere Business Continuity Advanced Failover.

460
 461 Only select STRONG STAR Data and Statistics Services personnel have direct access to the data on a "need to access
 462 basis"; for example (but not limited to) detecting and repairing data corruption and producing reports not currently within
 463 the STRONG STAR system. STRONG STAR Data and Statistics Services also follows the Principles Of Least Privilege
 464 (POLP). All user activity is tracked and recorded within the system so if any records are added, altered, or viewed the
 465 action is recorded and can be recalled for auditing purposes. Access to this information will require a password-protected
 466 login available only to authorized STRONG STAR Data and Statistics Services staff.

467
 468 Every member of the Research Team will be trained and monitored about how to handle and protect both medical and
 469 research records. Furthermore, the Research Team strictly controls access to study data.

470
 471 The STRONG STAR Data Safety and Monitoring Plan (DSMP) that has been developed in accordance with the National
 472 Institutes of Health Office of Human Research Protection to assure the appropriate clinical safety monitoring of study
 473 subjects participating in research will be used to monitor this study.

474 475 7.4. Statistical Consideration

476 477 7.4.1. Sample Size Estimation.

Estimate Required Sample Size (Completed / Evaluable)	24
Estimate Participant Drop Out / Withdrawal after Randomization/Inclusion	4 (17%)
Total Required to Randomize / Include	28
Estimate Participant Screen Fail / Exclusion	12 (30%)
Total Required to Consent	40

478
 479 7.4.2. Primary (i.e., primary outcome variables) and secondary endpoints
 480 **Health Questionnaire and Self-Report Measures:** The primary aim of this pilot is to explore the potential feasibility,
 481 safety, and effect of CBD in reducing PTSD symptoms compared to placebo in retired service members receiving mPE.
 482 Therefore, the primary outcome variables will be the CAPS-5 total score, the PCL-5 total score, and adverse event

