559 procedures can reduce the risk of contamination, clerical error, infection, injury, misuse of appropriate blood-sampling
560 devices, and risk when transporting laboratory samples.
561

562 Risks to Confidentiality

563 With the handling of medical and research records there is always the possibility of a breach of confidentiality. We will
564 maintain patients' names, contact information (i.e. Identifiers), and all PHI (protected health information) in an encrypted
565 computer database and all PHI identifiers will be removed in the database during data analysis. Every member of the
566 Research Team is carefully trained and monitored about how to store, handle, and protect participant records.

567

568 Risks of PTSD Diagnosis regardless of Treatment:

569 Possibility of increased suicidal risk. One of the risks of PTSD both in and out of treatment is attempted suicide, which can
570 result in death.

571

572 Safeguards for Protecting Participants:

573 CBD: Participants will be required to complete a liver function test (LFT) or provide a copy of recent LFT lab results
574 (completed within the last 90 days) to the study team prior to randomization to be considered for study eligibility. To
575 mitigate unnecessary LFTs, candidates will complete the full assessment to determine eligibility. If the candidate is
576 deemed eligible, the final step of the assessment process will be to complete an LFT or provide a copy of a recent (LFT).
577 The study team will work with the candidate to obtain LFTs and pay for them if necessary. All LFT labs will be reviewed
578 by [name] to determine study eligibility. Participants with enzyme levels 3x the normal limit will be excluded from the
579 study.

580

581 CBD, like most drugs, can lead to AEs and has drug-drug interactions. To safeguard against potential risk, we have
582 developed exclusionary criteria related to the individual's medical history and concomitant medication regimen.
583 Participants prescribed medications listed in the exclusion criteria will be excluded. Exceptions will be made for
584 participants taking the antidepressants Trazodone and Mirtazapine, a benzodiazepine just as needed, and/or stable doses
585 of the platelet inhibitors Clopidogrel or Warfarin. These participants will be monitored for AEs on a more frequent basis
586 (daily at each session). Additionally, consultation between the study team and [name] may occur on a more regular basis

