613 PTSD & PE: Psychological distress experienced by participants is expected to be temporary and participants will be
614 provided immediate coping tools and techniques to manage distressing emotions by the study therapist. Any indication
615 that the participant is considering suicide, endorses active psychosis/mania, or other harm to self/others will be handled
616 using evidence-based procedures and policies developed by the STRONG STAR Consortium. Participants who endorse
617 mania/psychotic symptoms will prompt a clinical interview with a licensed clinical provider to assess current risk and risk
618 of active mania/psychosis during study participation. Individuals with active mania/psychosis will be excluded from study
619 participation. Trained clinicians and evaluators will assess history of suicide and current suicidal ideation using the

620 Suicidal Ideation Thoughts and Behaviors Interview at the baseline assessment. For participants identified as having low
621 to moderate risk for suicide based on the assessment results, the patient will be maintained on protocol and additional risk
622 management procedures will be implemented within the context of the study treatment. For participants identified as being
623 at high risk for suicide based on the assessment results, disenrollment will be considered if it is unlikely that standard
624 treatment plus additional risk management procedures will maintain safety. High risk participants who are disenrolled
625 from the study will be referred for more intensive treatment (outpatient or inpatient).
626

627 If the research team feels that hospitalization should be considered, the participant's primary care provider or unit will be
628 contacted to escort the individual to the ED. If a participant reports experiencing psychotic or mania symptoms, or reports
629 dangerous amounts of alcohol and/or substance use, additional assessment by a licensed provider for consideration of
630 referral for clinical care and for disenrolling participants from the study will be conducted.
631

632 Enrolled participants will be monitored for AEs by the study therapist at Interim Assessment 1 (PE Session 1), Interim
633 Assessment 2 (PE Session 5), Interim Assessment 3 (PE Session 10), and at the 1-month follow-up. [name] and study
634 team members will meet each week to review reported AEs and to consult on potential behavior health risks. For urgent

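### Scheduled adverse-event questioning is unequal (4 occasions against 11 to 13), so the rate judged against <5% partly reflects how many participants are asked daily

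*Combined protocol and SAP*

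**What the plan says.** Section 7.4.2 makes AEs a primary outcome: "the primary outcome variables will be the CAPS-5 total score, the PCL-5 total score, and adverse event" monitoring. Hypothesis 1 (Section 3) sets an absolute criterion: "Combining CBD with mPE will be safe based on minimal (< 5%) adverse events and no serious adverse" events related to treatment. It does not say whether the 5% counts participants, events or visits, or whether relatedness applies to all AEs or only to serious ones.

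Section 8.1 gives the schedule for everyone: "Enrolled participants will be monitored for AEs by the study therapist at Interim Assessment 1 (PE Session 1), Interim", continuing "Assessment 2 (PE Session 5), Interim Assessment 3 (PE Session 10), and at the 1-month follow-up". An earlier paragraph of the same section gives the same four occasions.

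Section 8.1 then sets a denser schedule for participants admitted while taking trazodone or mirtazapine, an as-needed benzodiazepine, or a stable dose of clopidogrel or warfarin: "These participants will be monitored for AEs on a more frequent basis", specified as "daily at each session". The note to the Section 7.3 table agrees: "Daily Adverse Event monitoring to occur if participant taking one of the identified medications warranting additional monitoring". Section 8.1 also names AE monitoring at every visit as an added procedure when a participant is judged to be at risk, so the densely monitored group may extend beyond the listed drugs.

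Section 7.4.3 addresses the safety hypothesis with descriptive statistics. It sets no common set of occasions, makes no allowance for the number of times a participant was asked, and plans no split by monitoring intensity. Section 9.1 refers AE assessment to a standard operating procedure that is not part of the documents.

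**The concern.** A recorded AE rate depends on what happened to participants and on how closely they were asked. When a rate is held against a fixed threshold, randomisation gives no protection: even with perfectly balanced arms, the overall figure moves with the share of participants on the dense schedule. Participants on the listed drugs are also those in whom an interaction is suspected. A higher recorded rate in them would mix true risk with closer questioning, and the plan has no table that would separate the two. The pilot is meant to inform a larger trial, which could carry the figure forward.

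**Working it through.** **Is there a plan figure to reproduce?** No. The 5% is stated without derivation.

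**Step 1: count the scheduled occasions**, using study days from the Section 7.3 table.

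- Standard schedule: Days 4, 8, 15 and 45, so 4 occasions, 3 of them within Days 1-18.
- Dense schedule by the Section 8.1 text: ten sessions (Days 4-8 and 11-15) plus Day 45, so 11 occasions, 10 of them within Days 1-18.
- Dense schedule by the table: the marked cells add Days 1 and 18, so up to 13 occasions, 12 of them within Days 1-18. The AE row shows no one-month entry as extracted. The text includes that visit, so it is counted.
- Ratios: 11/4 = 2.75 and 13/4 = 3.25 overall; 10/3 = 3.3 and 12/3 = 4 during dosing.

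**Step 2: what <5% allows, if it counts participants.**

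- Of 24: 1/24 = 4.2% passes; 2/24 = 8.3% fails.
- Of 28 (the number to be randomised): 1/28 = 3.6% passes; 2/28 = 7.1% fails.
- CBD arm of 12 alone: 1/12 = 8.3% fails, so none is allowed.

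One additional participant with an AE is therefore enough to change the conclusion.

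**Step 3: illustration.** Assume each asking records an AE with independent probability q. Neither q nor independence comes from the documents. The probability of at least one recorded AE over k occasions is 1 - (1 - q)^k.

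| q (assumed) | k = 4 | k = 11 | k = 13 |
|---|---|---|---|
| 0.5% | 2.0% | 5.4% | 6.3% |
| 1% | 3.9% | 10.5% | 12.2% |
| 2% | 7.8% | 19.9% | 23.1% |
| 5% | 18.5% | 43.1% | 48.7% |

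**Step 4: effect on Hypothesis 1 at q = 1%.** With m of 24 on the dense schedule, the expected share with an AE is [m·p(k) + (24 - m)·p(4)]/24. For m = 6 (assumed) and k = 11 this is (6 × 0.1047 + 18 × 0.0394)/24 = 5.6%; for k = 13 it is 6.0%. With m = 0 it is 3.9%. The chance that at most 1 of 24 has a recorded AE is:

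- m = 0: 0.9606^24 + 24 × 0.0394 × 0.9606^23 = 76%
- m = 3: 66-68%
- m = 6: 57-61%
- m = 12: 41-47%

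Underlying safety is the same in every line; only the mix of schedules changes.

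**Step 5: chance imbalance between arms.** Take 6 of 24 on the dense schedule (assumed) and simple 12/12 allocation, ignoring the actual blocks and strata. The hypergeometric probability of any split other than 3:3 is 64%, and of 5:1 or 6:0 is 15.5%. The rest, about 49 points, is a 4:2 split. The expected arm difference this creates at q = 1% is 2 × (0.105 - 0.039) = 0.13 participants for a 4:2 split with k = 11, and 4 × (0.105 - 0.039) = 0.26 for a 5:1 split.

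**The case against.** The strongest reply is that Step 3 assumes its own mechanism. It treats each asking as a fresh draw and gives the one-month visit the same yield as a one-day interval. The documents state no recall period. If the question at session 5 covers everything since session 1, the gap shrinks to events forgotten or not mentioned. This stands: the size is not derivable, and the table above is only an illustration.

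It can also be said that unequal asking need not be what decides Hypothesis 1. At an assumed 2-5% per asking, the four shared occasions alone give 8-19% with an AE. With nobody on the dense schedule, the chance of at most 1 of 24 is then 43% at 2% and 5% at 5%. This also stands. Asking frequency is pivotal only if the yield is low, and the undefined unit of the 5% is a weakness in its own right.

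A reader might infer that the schedule biases CBD against placebo. The documents do not support that. The dense schedule follows baseline medication or judged risk, under double blinding. Medication is not a stratification factor, so chance imbalance is possible, but Step 5 puts its expected effect well below one participant at a 1% yield.

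Finally, the plan does not expressly say that both groups are pooled into one rate; a split by monitoring group would be compatible with its descriptive analysis. But no split is planned, and Hypothesis 1 names a single percentage.

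Extra monitoring of participants at higher risk is legitimate and is not at issue.

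**Conclusion.** The concern holds in a limited form. A primary outcome with an absolute criterion rests on 4 scheduled occasions for most participants and 11 to 13 for others, and nothing in the plan equalises or separates them. If the criterion counts participants, one extra recorded AE can reverse the conclusion on Hypothesis 1. The recorded rate therefore partly reflects the share asked daily. By how much is unknown, because it depends on the number on listed drugs, the yield per asking and the recall period, none of which is given. At an assumed 1% yield the contrast is about 4% against 10-12%. The documents do not support a claim of systematic arm bias, or a claim that unequal asking by itself settles Hypothesis 1. This is an inexpensive improvement to how a primary outcome is measured.

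**What to change.** Leave the extra clinical monitoring as it is. Put the same AE question, worded to cover the time since the last asking, on the session form for every participant at each of the ten PE sessions. With the one-month visit, Hypothesis 1 and the summary by arm then rest on one schedule of 11 occasions.

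Tabulate all AEs by arm and by monitoring group, and list those recorded at any remaining extra occasions, such as Days 1 and 18 in the table. Reconcile the occasions given in the Section 8.1 text with those marked in the Section 7.3 table, and state what the 5% counts.

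Do not restrict the rate to AEs first found at the four shared visits. An event recorded at session 2 might also have been reported at session 5, and dropping it would remove events from the participants at highest interaction risk.

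The cost is about a minute per session at visits everyone already attends, plus one table. The recorded AE rate may be somewhat higher, which makes <5% harder to meet.
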